## **Impact of ARIA-E MRI finding on the primary outcome**

In this supplementary analysis, the objective is to estimate the treatment effect, in the hypothetical scenario where ARIA-E would not have occurred. This analysis aims at removing the potential impact of ARIA-E on the primary endpoint.

All the attributes from the primary estimand will remain the same, but an ICE of 'ARIA-E occurrence' will be added. The 'ARIA-E occurrence' will be handled with hypothetical strategy. All data collected after the occurrence of an ARIA-E will be removed and treated as missing for this data analysis purpose. Post- ARIA-E data will then be imputed under the Missing at Random assumption unless ARIA-E is not the first ICE. In this case, the imputation will be determined by the strategy for the first ICE as described for the main estimator.

### **5.3.6 Convergence Considerations for RBMI-Based Analyses**

*In the rare situation that the imputation model (see step 1, imputation model, in Section 5.3.3) would fail to converge despite the attempt to simplify the variance-covariance*

matrix, it will be investigated whether removing some covariates and/or pooling factor levels of categorical covariates would solve the issue.

In case the root cause of the problem could not be attributed to the choice of covariates, the following approaches will be tried in sequence:

- *Replace jackknife with bootstrap, and accept up to a maximum of 5% failed runs (out of the total number of bootstrap runs). Runs that did fail would be discarded.*
- *Derive only a point estimate based on the conditional mean imputation, but no standard error (as jackknife and bootstrap did not work)*

#### **5.4 SECONDARY ENDPOINTS ANALYSES**

The same primary estimand's analysis strategy (see Section 5.3.2) will be applied to secondary endpoints listed in Table 5, with the following exceptions for the corresponding estimator:

- *. the imputation model will not include, as covariates, the baseline ADAS-Cog 13 total score and the baseline ADCS-ADL total score*

*The imputation model will thus include treatment group, visit, and treatment-by-visit interaction, the baseline score and the baseline score-by-visit interaction, and the randomization stratification factors, namely: disease stage, geographic region, the use of AD medication at baseline and the APOE ε4 status*

- *the analysis model will not include, as covariates, the baseline ADAS-Cog 13 total score and the baseline ADCS-ADL total score*

*The analysis model will thus include treatment, the baseline score and the randomization stratification factors, namely: disease stage, geographic region, the use of AD medication at baseline and the APOE ε4 status*

In the following, confirmatory secondary endpoints refer to endpoints included in the type I error control procedure. Other important secondary endpoints not subject to the type I error control procedure are considered as supportive secondary endpoints. For all secondary endpoints, the treatment effect over time will also be considered and the change from baseline to Weeks 24, 52, 76, and 104 will be provided as supplementary analyses.

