## **3. SAMPLE SIZE DETERMINATION**

Determination of sample size is based on participants enrolled in the global enrollment phase. In each study, approximately 1016 participants will be enrolled and randomized in 1:1 ratio to each treatment arm (active drug or placebo) during the global enrollment phase. The original planned sample size was of 760 participants, but it was increased to 1016 participants based on considerations from external studies (in protocol version 3).

Additional participants may be randomized during the China extension if at least 1 participant is enrolled at sites in mainland China, Hong Kong, or Taiwan that are recognized by the NMPA during the global enrollment phase.

The estimated sample size required to demonstrate efficacy with regard to Clinical Dementia Rating-Sum of Boxes (CDR-SB) is based on the following assumptions:

- the mean change in the CDR-SB from baseline to Week 104 is 2.5 points in the placebo arm
- a common standard deviation across treatment arms for change of approximately 2.97 from baseline to Week 104 in the CDR-SB
- active drug has a true effect of a 30% relative reduction in deterioration of CDR-SB

Based on these assumptions, and using a student's T-test with equal variance, a sample size was calculated for 90% power to detect a true treatment effect of 30% relative reduction in deterioration of CDR-SB at a two-sided  $\alpha$  of 0.05.

Uncertainties on parameters affecting the power (e.g., dropout rate, study drug discontinuation rate, standard deviation, and placebo decline) were assumed to be equivalent to a drop in sample size of up to around 35% and were corrected for accordingly. This calculation leads to a total of 1016 participants in the study.

At the date of writing Protocol Version 4, it was expected that participants would miss an average of 8 weeks of study drug administration over the course of the original two-year study due to the COVID-19 pandemic. This had the potential to decrease the power of the study from ~90% to ~80%. To mitigate the impact of missed administrations, the double-blind treatment period has been extended by 12 weeks. Under current assumptions, this brings the study power back to the originally planned ~90%.

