The efficacy analyses will be based on the ITT analysis set (see [Table 2](#)) and will compare the active drug arm against the placebo arm with regards to mean change from baseline to Week 116. Two-sided test hypotheses will be defined in the following sections and the type I error level will be 5%. There are two identical Phase III studies, for each respective study the type I error level will be 5%. In order to protect the overall type I error rate (i.e., at each study level) when incorporating the hypothesis testing of multiple endpoints into the analysis, a fixed sequence testing procedure ([Westfall and Krishen 2001](#)) will be used to adjust for multiple comparisons. Testing of each hypothesis will follow a pre-specified order such that an endpoint would only be tested if the preceding one in the hierarchy was significant at 5% alpha level. The endpoint hierarchy, starting with the primary endpoint and including only confirmatory secondary endpoints, is the following:

1. CDR-SB (Clinical Dementia Rating, Sum of Boxes)
2. ADAS-Cog 13 (Alzheimer's Disease Assessment Scale, Cognitive subscale, 13-item)
3. ADCS-ADL (Alzheimer's Disease Cooperative Study, Activities of Daily Living scale) total score
4. FAQ (Functional Activities Questionnaire)

Missing outcome data will be handled using data imputation aligned with the estimand, see Section [5.3.3](#) for a detailed description of the analysis strategy.

When using a statistical model with baseline covariate adjustment, missing baseline covariate data other than the baseline outcome measure will be imputed to the overall median value for continuous covariates, or will be imputed to the most frequent category for categorical variables. In addition, baseline covariates will be derived from information collected into the eCRF, unless otherwise specified.

In statistical models using change from baseline of a given outcome measure as the dependent variable, there will be no imputation of the baseline outcome value, with the consequence that participants missing the baseline outcome measure will not contribute to the analysis.

The impact of the COVID-19 pandemic on the study and its conduct will be monitored and the overall impact will be assessed and described in the Clinical Study Reports.

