#### *1. Imputation model*

The imputation model is a mixed effects model for repeated measures (MMRM) with the longitudinally assessed change from baseline in CDR-SB as the dependent variable. Its purpose is to estimate mean trajectories and covariance matrices of longitudinal outcomes in the placebo and active drug arms, respectively, while subjects remain on their randomized treatment. Therefore, all data after withdrawal from study treatment will be removed and considered as missing for the purpose of estimating the imputation model, and for this purpose only. If these data were not excluded, then the imputation model would estimate mean trajectories based on a mixture of observed pre- and post-discontinuation data. These would not be compatible with the CIR assumption employed in the subsequent imputation step, which requires combining mean trajectories while on active drug up to the ICE with increments while on placebo thereafter, respectively.

The imputation model includes the following covariates: treatment group, visit, and treatment-by-visit interaction, baseline CDR-SB score and baseline CDR-SB score-by-visit interaction, baseline ADAS-Cog 13 total score, baseline ADCS-ADL total score and the randomization stratification factors, namely: disease stage (from the eCRF), geographic region (from the IxRS), the use of AD medication at baseline (derived from the eCRF based on a search of medications; see below for more details) and the APOE  $\epsilon$ 4 status (from the Vendor). For geographic region, IxRS is preferred over the eCRF source, to keep the “starting” region for analysis, in case a participant moved to a different region during the study (the eCRF would otherwise reflect the “final” region). AD medication at baseline will be defined as any use of donepezil, galantamine, memantine or rivastigmine prior to randomization and with an

end date not before the randomization date. An unstructured variance-covariance structure will be applied to model the within-subject errors across visits. If the model fails to converge, then a heterogeneous Toeplitz covariance structure will be used instead and if this still fails, then a compound symmetry covariance structure will be used.

Imputations will be based on restricted maximum likelihood (REML) estimation of the regression and covariance parameters from the imputation model ([von Hippel and Bartlett 2021](#); [Wang and Robins 1998](#)).

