#### **5.4.1 Confirmatory Secondary Endpoints**

The confirmatory secondary endpoints are provided to increase the confidence in the treatment effect observed on the primary endpoint. For these confirmatory secondary endpoints, *as already outlined in the beginning of Section 5.4, the same primary estimand's strategy will be applied, with some changes to the corresponding estimator (see Section 5.4 for the details).*

For these confirmatory secondary endpoints, MMRM analyses will also be considered as supplementary analyses. In this case, the change from baseline in the confirmatory secondary endpoints will be adjusted on the following covariates: treatment group, visit, treatment-by-visit interaction, the respective baseline score for each secondary endpoint, the baseline score-by-visit interaction and the randomization stratification factors as specified for the primary endpoint, see Section 5.3.4, paragraph on MMRM.

The method for controlling the overall Type I error is described in section 5.1.

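### The confirmatory secondary models omit the other baseline scales that the primary model uses, giving up some precision that could be had at no cost

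*SAP*

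**What the plan says.** For the primary endpoint, the imputation model in SAP section 5.3.3 adjusts for "baseline CDR-SB score and baseline CDR-SB score-by-visit interaction, baseline ADAS-Cog 13 total score, baseline ADCS-ADL total score and the randomization stratification factors". The ANCOVA in the analysis step uses the same baseline scores and factors.

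Section 5.4 carries this strategy over to the secondary endpoints with two exceptions. One is that "the analysis model will not include, as covariates, the baseline ADAS-Cog 13 total score and the baseline ADCS-ADL total score"; the other says the same of the imputation model. What remains is treatment, the endpoint's own baseline (with a visit interaction in the imputation model), disease stage, region, AD medication use and APOE ε4 status. Baseline CDR-SB, the primary endpoint's own baseline, is not listed either.

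The supplementary MMRM in section 5.4.1 uses the same reduced set: "the respective baseline score for each secondary endpoint, the baseline score-by-visit interaction and the randomization stratification factors as specified for the primary endpoint". So no planned analysis of ADAS-Cog 13, ADCS-ADL total or FAQ uses the fuller adjustment. Section 5.4 gives no reason, and the amendment rationale describes its added detail only as a clarification.

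**The concern.** The sponsor judged that baseline cognition and function belong in the CDR-SB model in addition to that scale's own baseline. The same argument applies to a cognitive or functional endpoint, and the SAP does not say why it is not followed.

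These three endpoints are tested in fixed sequence after CDR-SB (section 5.1), so a miss at one step closes the steps behind it. Any precision left unused is lost where it would count.

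The imputation model matters too. Section 5.3.3 assumes missing at random for intermittent gaps, for gaps not tied to an intercurrent event, and for data after events not related to drug or condition. If another scale's baseline predicts both decline and missingness, leaving it out makes that assumption harder to defend. The planning scenarios in SAP Appendix 1 put 26% to 36% of participants as having an intercurrent event, and the tipping-point analysis in section 5.3.4 is specified for the primary endpoint only.

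**Working it through.** **1. The plan's own figure.** SAP section 3 gives a placebo change of 2.5 points, SD 2.97, a 30% relative effect, two-sided α of 0.05 and 90% power. The difference is 0.30 × 2.5 = 0.75.

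n per arm = 2 × (1.960 + 1.282)² × 2.97² / 0.75² ≈ 330, so 660 in total. Correcting for the 35% allowance, 660 / 0.65 ≈ 1016, which matches. This concerns CDR-SB only; no SD, effect or power is stated for any secondary endpoint, so it fixes only the sample size.

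**2. What each confirmatory endpoint keeps and lacks.**

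| Endpoint | Own baseline | Other baseline scales absent |
|---|---|---|
| ADAS-Cog 13 | kept | ADCS-ADL, CDR-SB |
| ADCS-ADL total | kept | ADAS-Cog 13, CDR-SB |
| FAQ | kept | ADAS-Cog 13, ADCS-ADL, CDR-SB |

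Disease stage stays in every model and is the only other severity adjustment.

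**3. Availability.** Protocol section 4.6.2 and Appendix 1, Table 1 schedule CDR, ADAS-Cog 13 and ADCS-ADL at baseline. SAP section 5.1 imputes a missing continuous baseline covariate to the median, so adding these terms removes nobody.

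**4. Size.** Let r² be the share of residual variance that the omitted scales explain, given the endpoint's own baseline and the stratification factors. The documents do not give it; 0 to 0.08 is an assumption. For complete-data ANCOVA:

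- SE with the scales added / SE under the SAP = √(1 − r²)
- equivalent extra participants = 1016 × (1/(1 − r²) − 1)
- power = Φ(2.80/√(1 − r²) − 1.96), where 2.80 = 1.96 + 0.84 stands for an assumed 80% power under the SAP model

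| r² | SE ratio | SE reduction | Equivalent extra participants | Power |
|---|---|---|---|---|
| 0 | 1.000 | 0% | 0 | 80.0% |
| 0.02 | 0.990 | 1.0% | 21 | 80.8% |
| 0.05 | 0.975 | 2.5% | 53 | 82.0% |
| 0.08 | 0.959 | 4.1% | 88 | 83.2% |

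From an assumed 90%, power would be 90.6% at r² = 0.02 and 91.4% at 0.05. The actual estimator adds conditional mean imputation and a jackknife, so these figures are approximate.

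**5. What the imputation already conditions on.** The imputation step uses each participant's observed outcomes. As an indication from the primary scale, the Appendix 1 correlation matrix implies that baseline alone explains 0.52² = 27% of Week 116 variance, and that all visits through Week 104 together explain 75%. Where earlier visits are observed, much of what another baseline scale could add may already be captured. No such matrix is given for the secondary scales.

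**The case against.** The strongest reply is that this is a valid, openly pre-specified model. Section 5.4 states the exceptions and lists the resulting terms, and the supplementary MMRM and the exploratory models follow the same rule. Change from baseline adjusted for own baseline and stratification factors is standard. That stands: the SAP does not contradict itself here, and what is at issue is efficiency and an unstated reason.

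A reader might infer that adjustment for baseline severity has been dropped. It has not. Own baseline stays, and ADAS-Cog 13 and ADCS-ADL each lose only one of the two scores named in the exceptions. Disease stage also stays, and Protocol section 3.3.1 requires evidence of functional decline for mild AD, so stage is a coarse measure of function and severity.

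A reader might also infer biased treatment effects from the missing data. The documents do not show that. Bias would need missingness to depend on the omitted score, given own baseline, stage and earlier visits, in a way that differs by arm. Missing data after drug- or condition-related events in the active arm are in any case imputed under copy increments from reference, which is explicitly not missing at random.

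Two practical objections remain. Extra terms could hinder convergence, but the primary model carries them already and section 5.3.6 allows covariates to be removed. For ADAS-Cog 11 and the ADCS-ADL instrumental score, adding the parent scale would create overlapping and probably near-collinear pairs. That second objection stands and limits the change to the three confirmatory endpoints.

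**Conclusion.** The point holds as a modest, free improvement. The confirmatory secondary models leave out baseline scales that are already collected and already used for the primary endpoint, without a stated reason.

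It would be too strong to say that the standard errors are necessarily larger in any material way, or that the tests are invalid. With complete data under 1:1 randomisation, omitting a prognostic baseline covariate leaves type I error unaffected. The precision cost depends on an r² that the documents do not give: from nothing at r² = 0 to a 4.1% SE reduction forgone at 0.08, or 0 to 3.2 percentage points of power from an assumed 80%. The effect on the missing-at-random assumption is one of plausibility only: conditioning on fewer variables asks more of that assumption, and the observed visits limit the loss.

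**What to change.** Before unblinding, amend SAP sections 5.4 and 5.4.1 for ADAS-Cog 13, ADCS-ADL total and FAQ only:

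- Include baseline CDR-SB, ADAS-Cog 13 and ADCS-ADL alongside the endpoint's own baseline and the stratification factors, in the imputation model, the analysis model and the supplementary MMRM.
- Keep the visit interaction for the endpoint's own baseline in the imputation model and the MMRM.
- Rely on the existing section 5.3.6 fallback if the imputation model does not converge.
- Leave the supportive secondary and exploratory endpoints as they are.

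The cost is a few lines of SAP text and two added terms for ADAS-Cog 13 and ADCS-ADL, or three for FAQ. No data are added and no participant is lost. If the sponsor has a reason for the smaller set, section 5.4 should state it. Either way the choice must be fixed in advance, because a covariate change made after unblinding would not be credible.

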**Table 5 Secondary Endpoints**

Secondary Efficacy Endpoint	Confirmatory	Type
Alzheimer's Disease Assessment Scale, Cognitive subscale, 13-item (ADAS-Cog 13)	yes	Continuous
Alzheimer's Disease Cooperative Study, Activities of Daily Living scale (ADCS-ADL) total score	yes	Continuous
Functional Activities Questionnaire (FAQ)	yes	Continuous
Mini Mental State Examination (MMSE)	no	Continuous
Alzheimer's Disease Assessment Scale, Cognitive subscale, 11-item (ADAS-Cog 11)	no	Continuous
Coding (Digit Symbol Substitution Test [DSST])	no	Continuous
Verbal Fluency Task	no	Continuous
Alzheimer's Disease Cooperative Study, Activities of Daily Living scale (ADCS-ADL) instrumental score	no	Continuous

ADAS-Cog 13= Alzheimer's Disease Assessment Scale, Cognitive subscale, 13-item; ADCS-ADL= Alzheimer's Disease Cooperative Study, Activities of Daily Living scale; ADAS-Cog 11= Alzheimer's Disease Assessment Scale, Cognitive subscale; DSST= Digit Symbol Substitution Test; FAQ= Functional Activities Questionnaire; MMSE= Mini Mental State Examination.

#### **5.4.1 Confirmatory Secondary Endpoints**

The confirmatory secondary endpoints are provided to increase the confidence in the treatment effect observed on the primary endpoint. For these confirmatory secondary endpoints, *as already outlined in the beginning of Section 5.4, the same primary estimand's strategy will be applied, with some changes to the corresponding estimator (see Section 5.4 for the details).*

For these confirmatory secondary endpoints, MMRM analyses will also be considered as supplementary analyses. In this case, the change from baseline in the confirmatory secondary endpoints will be adjusted on the following covariates: treatment group, visit, treatment-by-visit interaction, the respective baseline score for each secondary endpoint, the baseline score-by-visit interaction and the randomization stratification factors as specified for the primary endpoint, see Section 5.3.4, paragraph on MMRM.

The method for controlling the overall Type I error is described in section 5.1.

##### **5.4.1.1 Alzheimer's Disease Assessment Scale, Cognitive Subscale, 11- item and 13-Item (ADAS-Cog 11/ ADAS-Cog 13)**

The ADAS-Cog is the most frequently used scale to assess cognition in clinical trials for mild to moderate AD dementia ([Rozzini et al. 2007](#); [Connor and Sabbagh 2008](#); [Ihl et al.](#)

2012). More specifically, the ADAS-Cog is a participant-based assessment that measures learning and memory, language production, language comprehension, constructional praxis, ideational praxis, and orientation. The modified version will be used; it has 13 items and includes the addition of delayed word recall and a number of cancellation subtests, as well as use of only one trial for word recognition (Mohs et al. 1997). Equivalent alternate forms of the word recall, word recognition, and number cancellation subtests will be used in successive test administrations. The ADAS-Cog 11 and 13 will be used in this study, with ADAS-Cog 13 considered as a confirmatory secondary endpoint. Individual item scores are based on errors and generally range from 1 to 5, although some items have smaller or larger score ranges. The ADAS-Cog 13 total score ranges from 0-85, with higher scores reflecting greater impairment. It takes approximately 45 min to administer the ADAS-Cog 13.

#### **5.4.1.2 Alzheimer's Disease Cooperative Study, Activities of Daily Living Scale (ADCS-ADL), Total Score**

The ADCS-ADL (Galasko et al. 1997) is the scale most widely used to assess functional outcome in participants with AD (Vellas et al. 2008). The ADCS-ADL is a 23-item informant-based questionnaire that covers both basic activities of daily living (ADL) (e.g., eating and toileting) and more complex ADL or instrumental ADL (e.g., using the telephone, managing finances, preparing a meal). It has a 4-week recall period. Total scores range from 0-78, with higher scores indicating better functioning.

#### **5.4.1.3 Functional Activities Questionnaire (FAQ)**

The FAQ (Pfeffer et al. 1982) is an informant-based measure of functional abilities. Informants provide performance ratings of the target person on ten complex higher-order activities. The FAQ is a 30-point scale, the higher the score the worse the performance.

### **5.4.2 Supportive Secondary Endpoints**

For context, additional clinical endpoints collected longitudinally in the studies will be provided (see Table 5). The Sponsor proposes not to rank these hierarchically as for confirmatory secondary endpoints.

